## 4.0 TREATMENT PLAN

This study will assess whether oral pulsatile lapatinib dosing at the established MTD (2500mg BID, for two days) provides adequate intratumoral drug concentrations and EGFR inhibition for future studies that utilize 2 days on/5 days off regimen in EGFR-amplified high-grade glioma.

Extent of EGFR inhibition will be determined through comparison of EGFR phosphorylation in tumor tissue from patients receiving preoperative lapatinib (**Group A**) compared to a **Reference Group** of patients who do not receive preoperative lapatinib.

### 4.1 Treatment Schema

All patients must have recurrent EGFR-amplified high-grade glioma and be candidates for re-resection.

[figure not shown]
The first 8 patients on the study will be enrolled into Group A and receive lapatinib pre-operatively for 4 doses. Intratumoral drug levels will be analyzed following tissue sample collection during surgery. If adequate intratumoral drug concentration levels (1.5  $\mu$ M or higher) are reached in at least 3 of the initial 8 patients, the study will proceed with further enrollment as follows. See Section [11.0](#), Primary Objectives and Sample Size for details.

After the initial 8 patients are enrolled, subsequent patients will be sequentially assigned to either receive lapatinib pre-operatively for 4 doses (Group A) or to receive no drug prior to surgical resection ([Reference Group](#)): 20 patients will alternate enrollment into either Group A or the Reference Group (10 additional patients into Group A to complete the group, and 10 patients into the Reference Group); then 5 additional patients will enroll into the Reference Group to complete the group. Fresh and paraffin embedded tissue from surgical resection will be utilized for correlative studies.

#### Group A

Patients with recurrent, EGFR-mutated high-grade glioma who require surgical resection will receive a pre-operative course of lapatinib at a dose of 2500mg BID for four doses prior to scheduled surgical resection for recurrent high-grade glioma. Patients may take one extra dose for a total of 5 doses if unexpected logistical problems delay the surgery. Patients will take the last dose of lapatinib ideally 3-5 hours before surgery to resect the tumor. Tumor tissue will be snap-frozen for determination of EGFR phosphorylation and intratumoral drug concentration. Plasma samples will be collected at selected time points to determine plasma levels of lapatinib during surgery.

### Group A Treatment Plan

Patients should begin presurgical treatment with lapatinib starting 2 days (Day -2) prior to the day of scheduled tumor resection (Day 0). Doses of lapatinib should be taken 12 hours apart  $\pm$  2 hours. The first dose should be taken in the evening on Day -2, the second dose should be taken in the morning on Day -1, the third dose should be taken in the evening on Day -1, and the fourth dose should be taken on the morning of surgery. One additional dose is permitted 12 hours after the fourth dose  $\pm$  2 hours if unexpected logistical problems delay the surgery.

Patients who do not receive at least 4 doses of lapatinib prior to surgery will be replaced in the cohort; tissue from protocol surgery will no longer be required for these patients

but they may continue with post-surgical treatment provided any toxicity from pre-surgical dosing resolves within protocol parameters.

In order to accommodate biological sample collection and shipping, **surgery must take place Monday-Thursday**, with the exception of patients being treated at Memorial Sloan-Kettering Cancer Center: these patients may undergo surgery Monday- Friday (since tumor samples will be processed at MSKCC, these samples will not require overnight shipping).

Surgery, during which tumor tissue samples will be acquired, should be performed ideally within 3 to 5 hours after taking the last dose of lapatinib. The time that the last dose is taken on the day of tumor resection must be recorded. Patients whose last dose of lapatinib is greater than 12 hours prior to surgery (the time tumor tissue is removed) will be replaced in the cohort; tissue from protocol surgery will no longer be required for these patients but they may continue with post-surgical treatment provided any toxicity from pre-surgical dosing resolves within protocol parameters.

Research blood samples will be collected at baseline prior to the first presurgical dose and shortly before and after the time of surgery for determining the concentration of lapatinib in plasma. See Section [9.5.3](#) for details.

Tumor specimens will be analyzed for drug levels and a portion will be snap frozen for determination of EGFR phosphorylation. Instructions for collecting and handling tumor specimens are in Sections [9.5.1](#), [9.5.4](#), and [9.5.5](#).

Following surgery, patients will continue with standard post-operative management.

After recovery from surgical resection, patients will receive lapatinib post-operatively twice a day for two consecutive days every 7 days (2 days on/5 days off) in 28-day cycles.

Adequate recovery from surgical resection includes, but is not limited to, the following:

- No signs or symptoms of infections related to the surgical wound (*i.e.*, increasing erythema or cellulitis of the surrounding area, large amount of drainage, fever)
- Wound edges have healed

[figure not shown]
Post-operatively, patients must begin treatment within 30 days of surgical resection, and preferably within 3 weeks of the post-operative MRI; if more than 3 weeks elapse after the post-operative MRI, the patient will need a new MRI.

Patients will be followed by routine blood work, general and neurological examination, and MR imaging. See Section [9.1](#) for schedule.

Patients may continue to receive cycles of lapatinib until tumor progression, development of unacceptable toxicity, or meeting other criteria for going off treatment (Section [10.1](#)). Patients will be followed for adverse events for at least 30 days after the last dose of lapatinib. All patients will be followed for survival.

### **Reference Group**

Patients with recurrent, EGFR-amplified high-grade glioma who require surgical resection will go to surgery to resect brain tumor. A portion of tumor tissue will be snap-frozen for determination of EGFR phosphorylation.

### **Reference Group Treatment Plan**

Patients in this group will receive no study medication pre-surgically.

In order to accommodate biological sample collection, **surgery must take place Monday-Thursday**, with the exception of patients being treated at Memorial Sloan-Kettering Cancer Center: these patients may undergo surgery Monday- Friday.

Tumor tissue samples will be acquired during surgery to resect brain tumor. Tumor specimens will be snap frozen for determination of EGFR phosphorylation. Instructions for collecting and handling tumor specimens are in Sections [9.5.1](#) and [9.5.4](#).

Following surgery, patients will continue with standard post-operative management.

After recovery from surgical resection, patients will receive lapatinib post-operatively twice a day for two consecutive days every 7 days (2 days on/5 days off) in 28-day cycles.

Adequate recovery from surgical resection includes, but is not limited to, the following:

- No signs or symptoms of infections related to the surgical wound (*i.e.*, increasing erythema or cellulitis of the surrounding area, large amount of drainage, fever)
- Wound edges have healed

Post-operatively, patients must begin treatment within 30 days of surgical resection, and preferably within 3 weeks of the post-operative MRI; if more than 3 weeks elapse after the post-operative MRI, the patient will need a new MRI.

Patients will be followed by routine blood work, general and neurological examination, and MR imaging. See Section [9.1](#) for schedule.

Patients may continue to receive cycles of lapatinib until tumor progression, development of unacceptable toxicity, or meeting other criteria for going off treatment (Section [10.1](#)). Patients will be followed for adverse events for at least 30 days after the last dose of lapatinib. All patients will be followed for survival.

## 4.2 Treatment Requirements

All eligible patients who consent to this study must have a baseline pre-treatment MRI within 21 days prior to the initiation of treatment, and a post-surgical MRI within 21 days prior to starting Cycle 1.

Prior to every cycle patients must have:

- 1) ANC  $\geq$  1500/ $\mu$ l and platelets  $\geq$  100,000 / $\mu$ l.  
**AND**
- 2) All toxicities recovered to  $\leq$  grade 1 or  $\leq$  baseline

## 4.3 Drug Administration

Lapatinib treatment will be administered on an outpatient basis. No investigational or commercial agents or therapies other than those described below may be administered with the intent to treat the patient's malignancy.

Patients will be provided with a medication diary and instructed in its use. Group A patients will be instructed to bring all unused pills and their medication diary to the hospital on the day of surgery for assessment of compliance. During post-surgical cycles of lapatinib, all patients will be instructed to bring all unused pills and their medication diaries to each study visit for assessment of compliance.

#### 4.3.1 Lapatinib Administration

Lapatinib is an oral drug. Patients should take the lapatinib dose on an empty stomach, either 1 hour before or 1 hour after meals. Doses of lapatinib should be taken 12 hours apart  $\pm$  2 hours.

If a patient misses or vomits a dose, he or she should be instructed not to take or make up that dose. A dose will be considered missed, and should not be made up, if more than 2 hours have passed from the time the dose is normally taken.

Group A patients, pre-surgery: On the day of surgery the dose should be taken ideally 3-5 hours before scheduled surgery but no more than 12 hours prior to surgery (the time tumor tissue is removed). One additional dose is permitted 12 hours after the fourth dose ( $\pm$  2 hours) if unexpected logistical problems delay the surgery.

Grapefruit and grapefruit juice are prohibited while on this protocol.

#### 4.4 General Concomitant Medication and Supportive Care Guidelines

##### Prohibited Concomitant Medication During Study

*There must be a period of at least 10 days from discontinuation of prohibited drugs and initiation of therapy unless otherwise specified in the protocol. Requests for specific exceptions to the required wait time can be submitted to the ABTC Central Office by providing a pharmacological rationale that the washout period for a particular drug should be less than 10 days (or as specified in the protocol); this must be approved by the ABTC Central Office.*

In vitro studies with human liver microsomes indicate that lapatinib is metabolized by CYP3A4 and CYP3A5, and to a lesser extent CYP2C19 and CYP2C8. **Co-administration of lapatinib with potent or moderate CYP3A4 inhibitors (including grapefruit juice) and all CYP3A4 inducers is prohibited.** Assess risk/benefit before co-administering lapatinib with weak CYP3A4 inhibitors. CYP3A4 inhibitors may decrease lapatinib metabolism (increasing levels); while CYP3A4 inducers may increase lapatinib metabolism (decreasing levels).

In human subjects, lapatinib inhibited CYP3A4 and CYP2C8 at clinically relevant concentrations. Avoid co-administration of lapatinib with drugs that are substrates of CYP3A4 or CYP2C8 and have narrow therapeutic windows.

**Pgp inhibitors:** the following drugs are in vivo substrates of the P-gp transporter and may not be administered to patients receiving lapatinib: aliskiren, ambrisentan, colchicine, dabigatran etexilate, digoxin, everolimus, fexofenadine, imatinib, lapatinib, maraviroc, nilotinib, posaconazole, ranolazine, saxagliptin, sirolimus, sitagliptin, talinolol, tolvaptan, topotecan; clinically significant interactions have been demonstrated for the following drugs: digoxin, loperamide, saquinovir, and ritonavir.

Grapefruit and grapefruit juice are prohibited while on this protocol.

### Corticosteroids

Postoperatively, corticosteroids should be tapered to a stable dose as determined by the clinical status of the patient. Corticosteroid dose may, of course, be increased in the event of clinical deterioration or at the discretion of the attending physician. In the event of suspected clinical deterioration, repeat brain imaging is recommended.

### Antiemetics

The use of any antiemetic deemed necessary for the care of the patient is allowed.

### Anticonvulsants

For this study, patients may not be on enzyme-inducing anti-epileptic drugs (EIAED); patients who require anti-epileptic drugs (AED) may be on non-enzyme inducing anti-epileptic drugs (NEIAED). If a patient on this study protocol needs to have an AED started or needs to have a second AED added then only NEIAED should be used. There must be a  $\geq 10$  day period from discontinuation of an EIAED and initiation of therapy. In the event that an enzyme-inducing anti-epileptic drug must be used for a patient on study the patient will be removed from the protocol.

### Antidiarrheal

The use of any antidiarrheal is permitted. Lapatinib-induced diarrhea is most commonly treated with loperamide. Patients should be educated about how to use loperamide. See also Supportive Care below for management of diarrhea.

### Herbal and Non-Traditional Medications

No data exist regarding the interaction of lapatinib with commonly used herbal or non-traditional medications. Patients should be instructed not to use such medications while receiving lapatinib therapy.

### Supportive Care

#### **Diarrhea**

Early diarrhea management for patients taking lapatinib must be initiated as soon as the first episode of diarrhea has occurred. Close monitoring and proactive management of diarrhea is essential. At the time of starting lapatinib, all patients should be given a prescription for loperamide or analogue, and be advised to keep the prescription/medication with them at all times. The patient should be clearly instructed to start loperamide promptly at the first signs of diarrhea. A dose of 4 mg loperamide must be given after first episode of diarrhea, and 2 mg every 4 hours or after every episode of unformed stool, until the patient is free from diarrhea for 12 hours. The maximum allowed daily dose of loperamide is 16 mg. The patient must contact the investigator as soon as possible after diarrhea starts.

For Grade 3 or 4 diarrhea or Grade 1 or 2 with complicating features (severe cramping, severe nausea/vomiting, decreased performance status, fever, sepsis, Grade 3 or 4 neutropenia, frank bleeding, dehydration): use intravenous fluids as appropriate, consider hospital administration and use prophylactic antibiotics as needed (example fluoroquinolones) especially if diarrhea is persistent beyond 24 hours or there is a fever or Grade 3-4 neutropenia.

### **Rash**

There is no standard, known, or established treatment proven effective for drug-related skin rashes or changes due to lapatinib. If the rash is severe (1-3% of cases) then most commonly, a papular/pustular rash has been observed, which frequently improves even though the same dose of lapatinib therapy is continued uninterrupted. The need for oral or topical antibiotics is a clinical decision of the investigator and should be preceded by a culture of affected areas and, if indicated, a dermatology consultation. **Oral retinoids should not be given because of theoretical concerns about negatively affecting the lapatinib mechanism of action.** Oral steroids are also strongly discouraged. Other options for treatment of significant rashes may be determined upon consultation with dermatologist.

## **5.0 TOXICITY**

### **5.1 Toxicity Management and Dose Delay/Modification for Lapatinib**

Dose delays and dose modification requirements for clinically significant adverse events or abnormal laboratory values assessed as unrelated to disease progression, intercurrent illness, or concomitant medications are defined in the following sections. Toxicities must have an attribution of possible, probable, or definite to lapatinib (see Section [9.2.2](#)). Adverse events (AEs) should be treated with the appropriate maximum supportive care and should be clearly documented on the case report form.

Group A patients—pre-surgical treatment: Lapatinib is not dose-reduced for toxicities in the pre-surgical dosing period; if treatment is delayed for toxicity such that the patient cannot receive the four lapatinib doses according to the pre-surgical dosing schedule, or if

lapatinib is discontinued, the patient will be replaced in the cohort but may continue with post-surgical treatment provided toxicity from pre-surgical dosing resolves within protocol parameters.

All adverse events will be monitored and collected throughout the trial and documented based on CTCAE version 5.0. If there are three or more delays of scheduled surgery due to lapatinib-related serious adverse events (SAE) among the initial 8 patients; or if there are any surgical complications and delayed wound healing SAEs grade  $\geq 3$  considered lapatinib-related among the first three patients, ABTC investigators will consult with CTEP investigators and the pharmaceutical sponsor about such events. See Section [9.3](#) for SAE information.

## 5.2 Dose Modification/Reduction for Lapatinib

The dose levels and the general approach to lapatinib dose modification on this trial are shown below. Adverse events (AEs) should be treated with the appropriate maximum supportive care, and dose reductions should be clearly documented on the case report form.

If multiple toxicities occur, dose modification decisions should be based on the most severe toxicity.

Dosing will be held until the toxicity has resolved as specified in Table [5.2.2](#), Dose interruption or discontinuation due to LVEF, and Table [5.2.3](#), Toxicity management / Dose discontinuation due to AEs. The maximum length of time that lapatinib can be held for treatment-related toxicity is 14 days. If treatment-related toxicity is not resolved in  $\leq 14$  days, the patient will be removed from treatment. After resolution, when dose reduction is permitted, the dose of lapatinib will be modified as stipulated below, with a maximum of 1 dose reduction. If there is any question, the ABTC Central Office and the Study Chair should be contacted.

### Dose Reduction Table for Lapatinib

Dose Level	Lapatinib
Starting dose	2500 mg twice a day
First dose reduction	2000 mg twice a day

#### 5.2.1 Severe Cutaneous Reactions

Severe cutaneous reactions have been reported with lapatinib. If life-threatening reactions such as erythema multiforme, Stevens-Johnson syndrome, or toxic epidermal necrolysis (e.g., progressive skin rash often with blisters or mucosal lesions) are suspected, discontinue treatment with lapatinib.

#### 5.2.2 Lapatinib dose modification for LVEF events

##### General instructions for cardiac monitoring

[figure not shown]
- All patients must have an LVEF measurement of at least 50% by echocardiography or MUGA scan (preferably echocardiography), within 21 days prior to treatment start.
- The method used for LVEF assessment in an individual patient should be the same throughout the trial.
- Echocardiography must be performed under the supervision of an experienced cardiologist, preferably at the same high-volume laboratory for the duration of the trial. The guidelines of the American Society of Echocardiography will be used.
- Subsequent scheduled LVEF assessments can be performed every 12 weeks during treatment. Follow up LVEF assessment after discontinuation of therapy should be obtained if the findings are abnormal.
- In addition, any patient who develops clinical signs or symptoms of cardiac failure should undergo an LVEF assessment and an ECG.
- If there are two dose interruptions for an ejection fraction decrease from baseline, discontinue lapatinib.

**Table 5.2.2: Dose interruption or discontinuation due to LVEF**

System Organ Class (SOC) in CTCAE	CTCAE Term	Instructions
Cardiac Disorders	If symptomatic, please utilize CTCAE term “Left ventricular systolic dysfunction (LVSD)” or “Heart failure,” as appropriate	Permanently discontinue lapatinib.
Investigations	If asymptomatic, please utilize CTCAE term ”Ejection fraction decreased”	Refer to Figure below and instructions above.  If there are two dose interruptions for an ejection fraction (EF) decrease from baseline, discontinue lapatinib.

Algorithm for continuation and discontinuation of GW572016 (lapatinib) based on interval LVEF assessments for patients with New York Heart Association (NYHA) Class

I or II congestive heart failure.

Notes:

- Only one dose interruption for ejection fraction decrease will be allowed.
- All assessments will be compared to baseline ejection fraction at the start of the trial.

### 5.2.3 Lapatinib dose modification for non-cardiac AEs

Table 5.2.3:

Adverse Events	Grade	Action
Pneumonitis, Pulmonary fibrosis, Adult Respiratory Distress Syndrome (ARDS), Pulmonary edema (non-cardiogenic)	Grade 1 to 4	Patients who develop symptoms or signs suggestive of pulmonary infiltrates or pneumonitis, should have lapatinib interrupted while a thorough evaluation is performed. If pneumonitis is confirmed, permanently discontinue lapatinib. If other parenchymal abnormalities are confirmed and the relationship to lapatinib cannot be excluded, lapatinib must be permanently discontinued.
Rash	Grade 1	No dose modifications. See “supportive care for rash.”

Adverse Events	Grade	Action
	Grade 2	If toxicity is unacceptable to patient or medically concerning, hold lapatinib until recovery to $\leq$ Grade 1 for up to 14 days. Restart at the same dose.  If dose has previously been held for grade 2 toxicity and grade 2 symptoms recur, OR if the patient finds the symptoms unacceptable, hold dose until recovery to $\leq$ Grade 1. See “ supportive care for rash. ” Resume at one dose reduction..
	Grade 3	Hold lapatinib until recovery to $<$ Grade 1 for up to 14 days. See “ supportive care for rash. ” Resume at one dose reduction.
	Grade 4 rash or toxic epidermal necrolysis (e.g., Stevens-Johnson Syndrome, etc.)	Permanently discontinue lapatinib. See “ supportive care for rash. ”
Diarrhea	Grade 1	Continue lapatinib, but start loperamide (initial dose 4 mg followed by 2 mg every 4 hours or after every unformed stool). It is suggested to continue loperamide until the subject is free from diarrhea for 12 hours. See “ supportive care for diarrhea. ”
	Grade 2 to 4	Hold lapatinib until grade 1 or lower (up to 14 days). Start loperamide as above, and other measure. See “ supportive care for diarrhea. ” Resume at one dose reduction.
Abnormal liver function tests (ALT, bilirubin)	Grade 1 or 2 abnormal ALT / bilirubin	Lapatinib must be discontinued permanently for patients with: 1. BOTH bilirubin and ALT abnormalities being of Grade 2 OR 2. EITHER bilirubin OR ALT abnormality is Grade 2 and accompanied by signs or symptoms which, in the opinion of the treating physician, are related to liver injury caused by lapatinib. (Such signs and symptoms may include abdominal pain, fever, jaundice, rash, eosinophilia or a performance status (PS) drop of $\geq 1$ point from baseline.)
	Grade 3 to 4 abnormal ALT and / or bilirubin	Permanently discontinue lapatinib.
Other Grade 3 to 4 AEs or intolerable Grade 2 AEs due to lapatinib		Permanently discontinue lapatinib therapy.

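### Table 5.2.3 gives two different restart doses for a first Grade 2 rash that the patient finds unacceptable

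*Combined protocol and SAP*

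**What the plan says.** The Grade 2 rash cell of Table 5.2.3 (protocol Section 5.2.3) contains two instructions.

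- Paragraph 1: "If toxicity is unacceptable to patient or medically concerning, hold lapatinib until recovery to" Grade 1 or lower, for up to 14 days. The patient then restarts at the unchanged dose.
- Paragraph 2: "If dose has previously been held for grade 2 toxicity and grade 2 symptoms recur", or, as a second limb, "OR if the patient finds the symptoms unacceptable, hold dose until recovery to" Grade 1 or lower. The patient then resumes one dose level down.

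The Dose Reduction Table in Section 5.2 sets the starting dose at 2500 mg twice daily and has a single lower level, "2000 mg twice a day". Section 5.2 allows reductions "with a maximum of 1 dose reduction".

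**The concern.** The patient's own judgement that the rash is unacceptable is a trigger in both paragraphs, and the paragraphs end at different doses. Paragraph 1 does not say whether it is confined to a first episode. The second limb of paragraph 2 does not require an earlier hold. A first Grade 2 rash that the patient will not accept therefore satisfies both.

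Two sites could then restart identical patients at different doses, each following the text. The choice has a further consequence because only one reduction exists. Grade 3 rash and Grade 2 to 4 diarrhea in the same table also call for one reduction, so a patient reduced at a first Grade 2 rash has none left if either occurs later.

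**Working it through.** The plan states no figure on this point, so there is none to reproduce. The check is a comparison of the two paragraphs, followed by simple dose arithmetic.

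**Step 1: which paragraph applies to which case.** Three yes/no facts define the cases: an earlier hold for Grade 2 rash followed by recurrence (H), rash unacceptable to the patient (U), and rash medically concerning (M). Paragraph 1 is triggered by U or M. Paragraph 2 is triggered by H or U. There are 2 × 2 × 2 = 8 combinations of rule conditions. These are not counts of patients.

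| H | U | M | Paragraph 1 | Paragraph 2 | Result |
|---|---|---|---|---|---|
| no | no | no | no | no | no hold under this cell |
| no | no | yes | yes | no | same dose |
| no | yes | no | yes | yes (second limb) | **two doses** |
| no | yes | yes | yes | yes (second limb) | **two doses** |
| yes | no | no | no | yes (recurrence limb) | one reduction |
| yes | no | yes | yes, as general rule | yes (recurrence limb) | one reduction, specific limb governs |
| yes | yes | no | yes, as general rule | yes (recurrence limb) | one reduction, specific limb governs |
| yes | yes | yes | yes, as general rule | yes (recurrence limb) | one reduction, specific limb governs |

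The unresolved conflict is 2 of the 8 combinations. Both are first episodes that the patient finds unacceptable, and both arise from one clause.

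**Step 2: whether another rule settles it.**

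- Section 5.2: "If multiple toxicities occur, dose modification decisions should be based on the most severe toxicity". This ranks several toxicities. Here there is one.
- Last row of Table 5.2.3: "Other Grade 3 to 4 AEs or intolerable Grade 2 AEs due to lapatinib". Rash has its own rows, so this row does not reach it.
- Section 5.2: "If there is any question, the ABTC Central Office and the Study Chair should be contacted". This gives a route for a query but not a dose.

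**Step 3: size of the difference for a patient still at the starting dose.** Post-surgical dosing is twice daily, 2 days a week, in 28-day cycles (Section 4.1), so 2 × 2 × 4 = 16 doses per cycle.

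- Same dose: 2500 mg × 16 = 40,000 mg per cycle (2500 / 250 = 10 tablets per dose).
- One reduction: 2000 mg × 16 = 32,000 mg per cycle (2000 / 250 = 8 tablets per dose).
- Difference: 8,000 mg per cycle; 8,000 / 40,000 = 20%.

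For a patient already at 2000 mg twice daily, the same dose is 2000 mg and no further reduction exists, so this choice does not arise.

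**Step 4: the cell after the proposed rewording.** Paragraph 1 becomes (not H) and (U or M), which covers 3 combinations. Paragraph 2 becomes H, which covers 4. Neither applies in 1, and both apply in 0.

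**The case against.** The best defence is that the order of the cell shows the intent: a first hold with restart at the same dose, then a reduction on recurrence. On that view the symptoms in the second limb are the recurring ones. This is the more natural sequence and probably the intended one. It is not what the sentence says, because the capitalised alternative opens a new condition with no reference to an earlier hold. If the limb meant only recurring symptoms, it would also add nothing to the limb before it.

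The contact clause is a fair mitigation in a trial of 33 patients: a site that notices the overlap can get one central answer. A site that reads either paragraph alone, however, sees a complete instruction and has no reason to ask.

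A reader might go further and infer that neither paragraph is limited by episode, so that recurrences conflict too and 5 of the 8 combinations overlap. The documents do not support that. Paragraph 2 opens with a limb written expressly for a previous hold plus recurrence, and on an ordinary reading the specific rule governs over the general one. A first-episode limit on paragraph 1 would make this plainer, but recurrence is already covered.

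**Conclusion.** The point holds as a contradictory dosing instruction of narrow scope: a first Grade 2 rash, unacceptable to the patient, in a patient still at 2500 mg twice daily. The two branches differ by 20% of the dose, and one of them uses the single reduction.

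The severity is low. Both branches hold lapatinib until Grade 1 or lower and restart at a dose the protocol permits. Section 5.1 rules out dose reduction before surgery, so the primary PK and PD endpoints are untouched. What remains is post-surgical dosing, which feeds only the secondary results in Section 11.0 (adverse events, response, progression-free and overall survival). For lapatinib in general, Section 9.2.1 lists maculo-papular rash as likely (over 20%), but that is not a rate of unacceptable Grade 2 rash on this schedule. The 20% therefore describes one patient's dose and not an effect on the trial's results.

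The conclusion rests on two assumptions: that the Grade 2 toxicity named in paragraph 2 of the rash cell means rash, and that the specific recurrence limb takes precedence over paragraph 1.

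**What to change.** Reword the one cell at the next amendment.

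- Paragraph 1: open with 'First occurrence (no previous hold for grade 2 toxicity):' and leave the rest as it is, including restart at the unchanged dose.
- Paragraph 2: delete the second limb, on the patient finding the symptoms unacceptable. Keep "If dose has previously been held for grade 2 toxicity and grade 2 symptoms recur", the hold, the pointer to supportive care for rash, and the one-level reduction.

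The study chair should first confirm that this sequence was intended. If the intent was instead to let the patient's judgement lead to a reduction at first occurrence, keep the second limb and take the patient-acceptability trigger out of paragraph 1. That version also needs a few words saying that paragraph 2 governs when a first rash is both unacceptable to the patient and medically concerning, because that one combination would otherwise still meet both paragraphs.

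The cost is two sentences in one table cell and a short note to sites, with no added data, visits or procedures.
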